## **Study Protocol**

### *Study Design*

This study followed a randomized, double-blinded, crossover design. Participants reported to the clinical site on two separate visits. Participants were instructed to abstain from exercise on testing day and arrive at the lab fasted (no food or caffeine ingestion for 4 hours prior). Testing sessions consisted of two visits per week with a minimum of 24 hours between visits. During the first visit demographics and anthropometrics were assessed. At every testing each subject completed the following protocol: baseline Metabolic Rate and Respiratory Quotient. Immediately after baseline test, participants consumed supplement 1 or 2. Metabolic Rate and Respiratory Quotient Testing was repeated at 60, 120, and 180 minutes after supplementation. All participants underwent an informed consent process in accordance with the Declaration of Helsinki and an approved IRB protocol approved by institutional review board at Nova Southeastern University, IRB number 2024-209.

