### *Metabolic and Respiratory Quotient Testing*

An indirect calorimetry device (Parvo Medics TrueOne 2400) was used to measure RMR and RQ. The device was calibrated according to the manufacturer's instructions. Participants were instructed to lay completely still and relax for 15 minutes. The first 5 minutes was allotted for acclimatization. The Parvo Metabolic Cart measures the volume of oxygen consumed ( $VO_2$ ) and the volume of carbon dioxide produced ( $VCO_2$ ) by the patient on a breath-by-breath basis. The ratio of these gases is used to determine the Respiratory Quotient (RQ), providing information regarding substrate utilization. The parameters that were measured and used for analysis were RMR,  $O_2$  volume ( $VO_2$ ),  $CO_2$  volume ( $VCO_2$ ), the RQ, percentage of utilized fat (Fat%), and percentage of utilized carbohydrates (CHO%).

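### Exercise is restricted on the testing day only, so exercise the evening before can differ between a participant's two visits and add avoidable within-person noise (minor)

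*Combined protocol and SAP*

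**What the plan says.** The Study Design section describes a two-visit crossover: "This study followed a randomized, double-blinded, crossover design". The pre-visit conditions are "Participants were instructed to abstain from exercise on testing day and arrive at the lab fasted", with fasting defined as "no food or caffeine ingestion for 4 hours prior". The food and caffeine rule is thus a number of hours, while the exercise rule is tied to a calendar day. On spacing: "Testing sessions consisted of two visits per week with a minimum of 24 hours between visits". A baseline test is done at each visit, and afterwards "Metabolic Rate and Respiratory Quotient Testing was repeated at 60, 120, and 180 minutes after supplementation".

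The Metabolic and Respiratory Quotient Testing section lists the analysed parameters as RMR, VO2, VCO2, RQ, Fat% and CHO%. The Statistical Analysis section names a paired t-test of the two doses at baseline and a repeated-measures ANOVA by dose and time. The available text mentions no period term, sequence term or baseline covariate, and no recording or matching of prior exercise. That section breaks off mid-sentence and some front matter is not available, so these absences refer only to the text in hand.

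**The concern.** A crossover gains its precision from a participant's two visits being alike except for the dose. By restricting exercise at all, the protocol treats it as a disturbance to these measurements. A rule tied to the calendar day gives protection that depends on the appointment time, which is not stated: someone tested in the morning may train hard the evening before and comply fully.

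Two consequences follow if the effect of that exercise lasts until the test. Exercise before one visit and not the other adds within-person variation to every 100 versus 200 mg comparison. And the rule interacts with the 24-hour minimum gap: when visit 2 is the day after visit 1, the day before visit 2 is itself a testing day, while the day before visit 1 is never covered. That could produce a difference between visits, that is, a period effect.

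**Working it through.** The documents give no sample size, SD or effect size, so there is no figure of theirs to reproduce. Three checks were made.

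**1. Calendar check.** Inputs from the documents: exercise ban on the testing day, visits at least 24 h apart, tests of 15 min, last test 180 min after supplement. Visit length is about 15 + 180 + 15 = 210 min = 3.5 h. Assumed: start time 08:00 (range 07:00 to 12:00).

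- Before visit 1, exercise is allowed until midnight, so the shortest gap is 8 h (range 7-12 h).
- Before a next-day visit 2, with a whole-day ban, the shortest gap is 8 + 24 = 32 h if the 24 h run from start to start, or 8 + 24 + 3.5 = 35.5 h if from end to start (range 31-39.5 h).
- If the ban covers only the hours before the test, exercise later on the day of visit 1 is allowed. The gap before visit 2 is then 7-15.5 h and the asymmetry largely goes.
- If visits are two or more days apart, neither preceding day is covered.

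Evening-before exercise is therefore open before visit 1 on every reading. The contrast between visits needs both the whole-day reading and consecutive days.

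**2. Added variance of the unadjusted paired dose difference.** All inputs are assumed: a proportion p = 0.3 of unprotected visits preceded by exercise, RMR shift d = 2%, 4% or 6%, and day-to-day within-person SD of 4%. The reference variance is 2 × 0.04² = 0.0032.

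- Both visits unprotected, exercise independent: added 2p(1−p)d², ratio p(1−p)d²/0.0016.
- Next-day visits, only visit 1 unprotected, mean visit shift removed: added p(1−p)d², ratio p(1−p)d²/0.0032.
- Next-day visits, balanced sequences, no period term: the mean shift pd also enters the residual. The addition is p(1−p)d² + p²d² = pd², ratio pd²/0.0032.

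| d | Both visits, independent | Next-day, shift removed | Next-day, no period term |
|---|---|---|---|
| 2% | 0.21 × 0.0004/0.0016 = 5.25% | 2.6% | 0.3 × 0.0004/0.0032 = 3.75% |
| 4% | 0.21 × 0.0016/0.0016 = 21% | 10.5% | 0.3 × 0.0016/0.0032 = 15% |
| 6% | 0.21 × 0.0036/0.0016 = 47.25% | 23.6% | 0.3 × 0.0036/0.0032 = 33.75% |

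Sensitivity of the 21% figure: p = 0.2 gives 16% and p = 0.5 gives 25%. An SD of 3% gives 0.21 × 16/9 = 37%, and an SD of 5% gives 0.21 × 16/25 = 13%. If exercise habits correlate between visits with coefficient ρ, the independent-case increments are multiplied by (1−ρ). A 21% rise in variance is a standard error larger by √1.21 − 1 = 10%.

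**3. Bias.** A period difference π shifts the dose contrast by π(nA − nB)/N, where nA and nB are the numbers in the two sequences. With next-day visits, π = pd in size: 0.3 × 2% = 0.6 to 0.3 × 6% = 1.8 percentage points. With equal sequences the bias is 0. With a 60:40 split it is 0.2 × π = 0.12 to 0.36 points. A wider assumption (25-50% exercising, shift 1-5%) gives π = 0.25-2.5 points and a bias of at most 0.2 × 2.5 = 0.5 points at 60:40.

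**The case against.** The strongest reply is that nothing in the documents says exercise the evening before still affects RMR or RQ at the test. This stands: carry-over is an assumption, and the figures above are illustrations.

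Second, order is randomized, each visit has its own baseline, and the doses are compared at baseline. This stands in part. An effect long enough to reach the next day may change little over a three-hour session, and a same-visit baseline would remove that slow part well. But the available text does not say that the baseline enters the dose comparison, and the baseline t-test shows an average imbalance without correcting it. Any part that fades during the session would mix with the post-dose time course.

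Third, the variance figures may be too high. Habits may be correlated across visits, and the assumed 4% SD may already contain ordinary variation in prior exercise, in which case it is counted twice. Both points stand.

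A reader might infer that the protocol's own rules make the two visits systematically different and so bias the dose comparison. The documents do not support that. They do not show that any visits were on consecutive days, the exercise wording does not spell out that the whole calendar day is meant, and no sequence imbalance is reported. Without all three, this mechanism gives no systematic dose bias.

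**Conclusion.** The point holds as a minor one. Evening-before exercise is permitted, may differ between a participant's visits, and is not recorded in the available text. The harm is lost precision and a possible period effect, conditional on exercise still acting at the test. Under the stated assumptions the variance of the unadjusted paired difference rises by about 5-47% when exercise is independent before both visits. With next-day visits the rise is about 3-24% once the mean visit shift is removed, or about 4-34% if no period term is fitted. The two scenarios are alternatives for any one participant and must not be added. The true size cannot be computed from the documents, because the number of next-day pairs, the number who exercised and the duration of any effect are all unknown.

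**What to change.** **For future visits or a repeat study:** replace the calendar-day rule with no exercise for at least 24 hours before each visit, worded identically for both, and record the time of last exercise at arrival. The 24-hour length is a practical choice, not a figure from the documents. It would not fully equalise next-day visits, where the minimum abstention would be 24 h before visit 1 and about 48 h before visit 2, but both gaps would be at least 24 h. The cost is one sentence, one arrival question, slight burden on regular exercisers and an occasional rebooking.

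**For data already collected** (the protocol is written in the past tense): if last-exercise timing was recorded, repeat the dose comparison without participants who exercised the day before only one visit, as a sensitivity analysis. The cost is a smaller sample in that analysis. If timing was not recorded, report the spacing between visits and state uncontrolled prior-day exercise as a limitation.

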## **Statistical Analysis**

All data is expressed as mean SD. Basic descriptive statistics were used for participant demographics and anthropometrics. A paired t-test was used to assess any differences between the 100 and 200 mg doses for REE and RER at baseline. To determine the effects of Gyngerlean™ on energy expenditure, a repeated-measures analysis of variance (ANOVA) was used to determine differences between 100mg and 200mg doses for the 60, 120- and 180-time intervals. A repeated Dunnett's multiple

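### The 4-hour minimum fast permits a waning meal response during the session, so without a described control session, changes from baseline cannot be attributed to the product

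*Combined protocol and SAP*

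**What the plan says.** The Study Design section describes the trial as follows: "This study followed a randomized, double-blinded, crossover design". Participants must "arrive at the lab fasted (no food or caffeine ingestion for 4 hours prior" to testing. The available text sets no meal content, upper limit on the fast or time of day. It does not ask for the last meal to be recorded or for the two visits to be matched on it.

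Baseline comes first, then dosing: "Immediately after baseline test, participants consumed supplement 1 or 2". After that, "Metabolic Rate and Respiratory Quotient Testing was repeated at 60, 120, and 180 minutes after supplementation". The Metabolic and Respiratory Quotient Testing section gives the length of a test: "Participants were instructed to lay completely still and relax for 15 minutes". The outcomes analysed are RMR, the two gas volumes, and "the RQ, percentage of utilized fat (Fat%), and percentage of utilized carbohydrates (CHO"%).

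The Statistical Analysis section gives the aim as the product's effect on energy expenditure and names the method: the ANOVA "was used to determine differences between 100mg and 200mg doses for the 60, 120- and 180-time intervals". Baseline REE and RER are compared between doses by paired t-test. The section then breaks off in the middle of a sentence on a Dunnett procedure.

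**The concern.** Every outcome listed is a quantity that a recent meal changes. Four hours after eating, part of the meal response may remain, and over the next three hours it would be expected to fade. The fade runs in the same direction at each visit, so neither randomised order nor blinding removes it from a before-after change.

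Its effect differs by outcome. A falling meal response lowers energy expenditure and so works against detecting a real rise. It also lowers RQ and raises Fat%, which looks like a shift to fat use even if the product is inert. Residual caffeine could add to the drift in energy expenditure, but nothing in the documents allows that to be sized.

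This matters because of the stated aim. Both regimens described are active doses. A 100 versus 200 mg comparison answers a dose question, and would show nothing if both doses worked equally well. Anyone wanting the product's own effect will look at post-dose against baseline, the reading that the drift contaminates.

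**Working it through.** The documents state no sample size, SD, effect size or drift, so there is no figure of the plan's own to reproduce.

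**1. Clock times (inputs from the documents).** Assume that the last meal ended exactly 4 h before arrival and testing began on arrival. Baseline starts at 4.0 h and lasts 0.25 h, so dosing is at 4.25 h. Repeat tests start at 4.25 + 1 = 5.25 h, 4.25 + 2 = 6.25 h and 4.25 + 3 = 7.25 h. This is the earliest window that the rule permits. An 8-hour fast also complies and gives 8 to 11.5 h; a 12-hour fast gives 12 to 15.5 h.

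**2. Energy expenditure (all inputs assumed, none from the documents).** Meal-response rate in kcal/h at time t: (T/τ²) × t × exp(−t/τ). T is the total response, 6–10% of a 400–800 kcal meal (24 to 80 kcal). τ is the time of the peak, 1.0 to 2.0 h. Resting rate is 1600 kcal/day. Each test is evaluated at its midpoint, 0.125 h after it starts.

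- Largest fall at 4 h (T = 80, τ = 1.5). Baseline: 35.56 × 4.125 × exp(−2.75) = 9.38 kcal/h = 225 kcal/day. At 180 min: 35.56 × 7.375 × exp(−4.917) = 1.92 kcal/h = 46 kcal/day. Fall: 225 − 46 = 179 kcal/day, or 179/1600 = 11.2%.
- Smallest fall at 4 h (T = 24, τ = 1.0). Baseline: 24 × 4.125 × exp(−4.125) = 1.60 kcal/h = 38 kcal/day. At 180 min: 24 × 7.375 × exp(−7.375) = 0.11 kcal/h = 3 kcal/day. Fall: about 36 kcal/day before rounding, or 2.2%.

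| Fast | Fall by 180 min, kcal/day | % of 1600 |
|---|---|---|
| 4 h | 36 to 179 | 2.2 to 11.2 |
| 8 h | 1 to 49 | 0.1 to 3.1 |
| 12 h | 0 to 10 | 0 to 0.6 |

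By 60 min the fall at a 4-hour fast is already 23 to 98 kcal/day.

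A second assumed set (T = 40 to 80 kcal, τ = 1.0 to 1.5 h, resting rate 70 kcal/h) gives a fall of 3.6–10.6% by 180 min at 4 h. At 10 h the residual is at most 0.6% and the fall at most 0.5%. The 10-hour figure depends on τ. With the slowest curve of the first set (T = 80, τ = 2.0), 20 × 10.125 × exp(−5.0625) = 1.28 kcal/h and 20 × 13.375 × exp(−6.6875) = 0.33 kcal/h. The fall is 0.95 × 24 ≈ 23 kcal/day, or 1.4%.

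**3. Fat% (scale assumed).** On the linear scale Fat% = 100 × (1.00 − RQ)/(1.00 − 0.707), an RQ fall of 0.01 appears as 0.01/0.293 = 3.4 points of Fat%, and a fall of 0.02 as 6.8 points. This is only a conversion. Step 2 does not produce an RQ drift, and the documents give none.

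**4. The dose contrast.** With equal meals and fasts at both visits, the same residual is subtracted at each time and the drift contributes 0 kcal/day. If one participant ate 800 kcal (10% response) 4 h before one visit and 12 h before the other, the between-dose difference in change from baseline at 180 min would shift by 119 to 176 kcal/day over τ = 1.0 to 2.0 h. Over participants in randomised order, this is mainly added variance.

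**The case against.** The strongest reply is that the one efficacy analysis that can be read in full is immune to a shared drift. It is the comparison of doses, "on energy expenditure, a repeated-measures analysis of variance (ANOVA) was used to determine differences between 100mg and 200mg doses", at matching times. No legible sentence tests post-dose against baseline: the paired t-test compares doses, and the reference level of the Dunnett procedure is lost in the cut-off sentence. That loss is not a fault of the plan. All of this stands. The point therefore concerns what may be concluded from changes against baseline, not a demonstrated error in a stated test.

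A reader might infer that the rule puts every session 4 to 7 hours after a meal, so that drift is built into every change from baseline. The text does not support that. Four hours is a floor, longer fasts comply, and actual fasting times are not given. First-visit demographics and anthropometrics may also have delayed that baseline; their order is not stated.

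A reader might also want a false-positive rate for RQ in a before-after test. That would need an RQ drift, an SD and a sample size that the documents do not supply, for a test that they do not show. No such rate is claimed here.

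Finally, it can be said that the root problem is the lack of a control session, and that a longer fast would not cure it. That is correct. A longer fast removes much of one source of drift; it does not make before-after changes attributable.

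**Conclusion.** The concern holds in a limited form. The fasting rule permits a waning meal response during the measurement session, and the available text describes no placebo or untreated session that could separate it from a product effect. Within-dose changes from baseline in energy expenditure, RQ, Fat% and CHO% therefore cannot be attributed to the product. The same-time dose contrast is not biased by a shared drift; uneven fasting mainly makes it noisier.

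The direction is plausible, but the size is unknown. The 2–11% fall by 180 minutes applies only to a participant at the 4-hour minimum and rests on assumed meal size, response fraction, curve shape and resting rate. After 12 hours the same model gives at most about 0.6%. After 10 hours it gives at most about 0.5% with a peak by 1.5 h, and up to 1.4% with a peak at 2 h. The point is worth acting on because the remedy is cheap, not because harm to the stated analysis has been shown.

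**What to change.** **If sessions are still to be run:** in the Study Design section, replace the 4-hour rule with a standardised overnight fast of about 10 hours or more, with no caffeine over the same period, and the same morning start at both visits. Record the time of the last meal at each visit. The cost is morning-only appointments. This reduces the drift but does not replace a control session.

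**If the data are already collected**, as the past tense of the text suggests: confine the conclusion to the same-time 200 versus 100 mg contrast, and state that changes from baseline in energy expenditure, RQ, Fat% and CHO% are not attributed to the product. If last-meal times are on file, show the change-from-baseline results by hours since last meal as a sensitivity display. If the Dunnett procedure does compare with baseline, the same limit applies to its results. The cost is a narrower conclusion and one extra display, with no added participants, staff or readings.

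### No stated rule matches fasting length, last meal or start time between a participant's two visits, so avoidable residual variance can enter the 100 versus 200 mg contrast

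*Combined protocol and SAP*

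**What the plan says.** All of the relevant conduct text is in the Study Design section of the combined protocol and SAP.

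- Design: "This study followed a randomized, double-blinded, crossover design", and "Participants reported to the clinical site on two separate visits".
- Food and caffeine: participants are to "arrive at the lab fasted (no food or caffeine ingestion for 4 hours prior".
- Exercise: "Participants were instructed to abstain from exercise on testing day".
- Spacing: "Testing sessions consisted of two visits per week with a minimum of 24 hours between visits".
- Baseline: "At every testing each subject completed the following protocol: baseline Metabolic Rate and Respiratory Quotient". The supplement follows immediately.
- Follow-up: "Metabolic Rate and Respiratory Quotient Testing was repeated at 60, 120, and 180 minutes after supplementation".

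The Metabolic and Respiratory Quotient Testing section lists the analysed outcomes: RMR, the two gas volumes, RQ, Fat% and CHO%.

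The Statistical Analysis section compares the two baselines with a paired t-test and the two doses at 60, 120 and 180 minutes with repeated-measures ANOVA. The part that can be read mentions neither a change score nor a baseline covariate for the dose contrast. It breaks off at the Dunnett comparison.

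**The concern.** Four hours is a floor with no upper limit. The 24-hour minimum separates the visits but does not fix the time of day. A participant could be tested four hours after lunch on one occasion and after a whole night without food on another, and comply both times. By restricting food, caffeine and exercise, the protocol itself accepts that these conditions affect the outcomes. It states no rule holding them equal between one person's two visits, which is where the dose comparison is made.

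Stable differences between people cancel in a crossover. Differences between one person's visits do not: they are the error term of the 100 versus 200 mg contrast. Any part of that error due to unmatched preparation is avoidable, and it widens the confidence interval for the only randomised comparison described.

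**Working it through.** **No documented figure to reproduce.** The available text gives no sample size, SD, variance component, effect size or power. Everything below is an assumed range.

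**Model.** Set the single-reading variance within a visit to 1. Let s be the day-to-day (visit-level) variance within a person, taken as constant over a visit. The assumed day-to-day SDs of 0.5, 1.0 and 1.5 give s = 0.25, 1.00 and 2.25. The outcome is the mean of the three post-dose readings. Person effects cancel in the paired difference, and the factor 2 for two visits drops out of every ratio.

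- Unadjusted: V = s + 1/3.
- With the same-visit baseline as covariate: the baseline has variance s + 1 and covariance s with the post-dose mean, so V = s + 1/3 − s²/(s + 1) = s/(s + 1) + 1/3. The cost of estimating the slope is ignored.
- Narrowing of the interval = 1 − √(V after matching / V before matching).

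**Matching removes half of s**

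| s before → after | Unadjusted V | Narrowing | Adjusted V | Narrowing |
|---|---|---|---|---|
| 0.25 → 0.125 | 0.583 → 0.458 | 11.4% | 0.533 → 0.444 | 8.7% |
| 1.00 → 0.50 | 1.333 → 0.833 | 20.9% | 0.833 → 0.667 | 10.6% |
| 2.25 → 1.125 | 2.583 → 1.458 | 24.9% | 1.026 → 0.863 | 8.3% |

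**Matching removes a quarter of s**

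| s before → after | Unadjusted V | Narrowing | Adjusted V | Narrowing |
|---|---|---|---|---|
| 0.25 → 0.1875 | 0.583 → 0.521 | 5.5% | 0.533 → 0.491 | 4.0% |
| 1.00 → 0.75 | 1.333 → 1.083 | 9.9% | 0.833 → 0.762 | 4.4% |
| 2.25 → 1.6875 | 2.583 → 2.021 | 11.6% | 1.026 → 0.961 | 3.2% |

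If participants already came under similar conditions at both visits, matching removes almost none of s and the narrowing is near 0%.

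**Baseline adjustment alone, without matching.** Comparing adjusted with unadjusted V at the same s: 1 − √(0.533/0.583) = 4%, 1 − √(0.833/1.333) = 21%, and 1 − √(1.026/2.583) = 37%. Using the baseline already collected is therefore worth at least as much as matching in the two larger-s cases, and about as much as the weaker matching case when s is small.

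**What a baseline cannot remove.** A change score cancels a constant visit shift entirely, but not a drift over the session that itself depends on fasting length or time of day. Let q be the variance of that drift relative to the reading variance. At one post-dose time the change-score contrast has variance proportional to 2 + q. For q = 0.10, 0.25 and 0.50 this is 1.05, 1.125 and 1.25 times its value without drift.

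**Direction.** Randomised order and blinding give no reason for fasting length or clock time to be linked to dose, so the expected shift in the contrast is zero and only its variance grows.

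**The case against.** The strongest reply has four parts.

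1. *The design already has a safeguard.* A baseline is taken at every visit just before dosing, and it can absorb much of a visit-level shift. This stands in part. The readable analysis text uses the baselines only in a t-test between doses, which adjusts nothing. The text is cut off, though, so adjustment elsewhere cannot be excluded. Even with adjustment, one baseline reading is an imperfect measure of the visit shift, and drift remains.
2. *The size is assumed throughout.* This stands. In particular, nothing in the documents shows how much day-to-day variance comes from fasting or clock time.
3. *Silence is not evidence of mismatch.* This stands too. A reader might infer that visits were in fact unmatched, but the text shows only that no matching is stated. Booking practice may have achieved it.
4. *The study is reported in the past tense.* An instruction cannot be changed for visits already made, so for those the remedy reduces to reporting and adjustment.

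Two further inferences are tempting and should not be drawn. One is that a crossover is meant to remove this kind of noise. It removes stable differences between people, and between-visit variation is what remains. The other is that matching would repair the before-after changes in RQ and Fat%. Readings fall at no less than 4, 5, 6 and 7 hours since food at every visit, matched or not. That confounding of time since dose with time since food comes from the absence of any described placebo visit, which is a separate matter.

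**Conclusion.** The point holds as a loss of precision in the 100 versus 200 mg contrast. The stated rule lets a compliant participant attend under different conditions at the two visits, and the resulting shift adds residual variance. A reader might infer that the contrast is biased. With randomised order, the documents do not support that.

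On the assumptions above, matching narrows the interval by about 3% to 11% if the analysis adjusts for the same-visit baseline, by about 6% to 25% if it does not, and by close to nothing if visits were already alike. These figures rest on assumed variance ratios, an assumed share removed by matching, and a visit shift that is constant within a session. The improvement is worth making because it is cheap; it does not show that the trial's comparison is unsound.

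**What to change.** **For visits still to be made, or a future study:** require each participant's two visits to start at about the same clock time (within about 1 hour), after the same food- and caffeine-free interval and a repeat of the same last meal. Record start time, hours since food and hours since caffeine at each visit.

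**For the analysis:** adjust the dose contrast for the same-visit baseline, and say so in the Statistical Analysis section. This uses data already collected.

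**For completed visits:** report start times and hours since food and caffeine by visit if they were recorded, adjust for them where a participant's two visits differ, and state the lack of a matching rule as a limitation.

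**Cost:** less flexible booking, a line in the participant instructions and a few extra data fields per visit. No additional procedure is needed. If matching succeeds, the recorded times will differ little within a person and serve mainly as a check.

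### No record or repetition of prior-day diet is described, so diet can add visit-level noise to the raw 100 versus 200 mg comparison of RQ, Fat% and CHO%

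*Combined protocol and SAP*

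**What the plan says.** The Study Design section states: "This study followed a randomized, double-blinded, crossover design". Before each visit participants had to "arrive at the lab fasted (no food or caffeine ingestion for 4 hours prior"). The one other preparation rule is "Participants were instructed to abstain from exercise on testing day". On timing, "Testing sessions consisted of two visits per week with a minimum of 24 hours between visits". On data collection, "During the first visit demographics and anthropometrics were assessed"; diet is not listed. A pre-dose reading is taken both times: "At every testing each subject completed the following protocol: baseline Metabolic Rate and Respiratory Quotient".

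The Metabolic and Respiratory Quotient Testing section explains how RQ is read: "The ratio of these gases is used to determine the Respiratory Quotient (RQ), providing information regarding substrate utilization". It lists RQ, Fat% and CHO% among the parameters used for analysis.

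The Statistical Analysis section gives a paired t-test of the two doses at baseline for REE and RER. It then gives a repeated-measures ANOVA of 100 versus 200 mg at 60, 120 and 180 minutes, introduced as a test of effects on energy expenditure. The readable text stops as it introduces a Dunnett procedure. Up to that point neither change from baseline nor a baseline covariate is mentioned.

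**The concern.** A crossover removes whatever is stable within a person. What someone ate on the previous day is not stable: it can differ between the two visits, and the fuel burned at rest depends on recent carbohydrate and fat intake as well as on hours since the last meal. Two visits with the same 4-hour fast can therefore start from different RQ levels for reasons unrelated to dose.

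Such a shift belongs to the visit. It is shared by the 60, 120 and 180 minute readings, so averaging them does not shrink it, and it passes straight into the paired dose difference if post-dose levels are compared as they stand. At stake is precision for RQ, Fat% and CHO%: wider intervals, and a greater chance of missing a real difference between doses. No claim is made about RMR.

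**Working it through.** **1. Is there any diet control beyond the fast?** All three readable sections were checked. They contain no food record, repeated meal or prior-day instruction.

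**2. Does the plan give a figure to reproduce?** No. The readable text has no sample size, SD, effect size or power statement, so everything below is illustrative.

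**3. Assumed inputs (none from the documents).**
- SD between visits of the previous day's food quotient: 0.02 to 0.04, middle 0.03.
- Share carried into resting RQ: 25% to 50%, middle 40%.
- Residual SD of RQ, excluding diet (e): 0.02 to 0.03, middle 0.025.
- Fat% linear in RQ from 0.707 to 1.00, so the slope is 100/(1 − 0.707) = 341 points per RQ unit, or 3.41 per 0.01.

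**4. Diet SD in RQ (d) = food-quotient SD × share.**
- Low: 0.02 × 0.25 = 0.005, or 1.7 Fat% points.
- Middle: 0.03 × 0.40 = 0.012, or 4.1 points.
- High: 0.04 × 0.50 = 0.02, or 6.8 points.

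**5. Raw post-dose comparison.** At one time point the paired difference has variance 2(e² + d²), against 2e² with diet fully matched. The ratio is 1 + k, where k = (d/e)².

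**6. With the same-visit baseline as covariate.** Suppose baseline and post-dose readings share d and have independent errors with SD e. Then the variance is 2(e² + d²)(1 − r²), with r = d²/(d² + e²). The ratio to 2e² simplifies to 1 + k/(1 + k).

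**7. With change from baseline.** The variance is 4e², so the ratio is 2 whatever the diet SD.

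| d | e | k | Raw | Covariate | Change |
|---|---|---|---|---|---|
| 0.005 | 0.03 | 0.028 | 1.03 | 1.03 | 2.00 |
| 0.012 | 0.025 | 0.230 | 1.23 | 1.19 | 2.00 |
| 0.02 | 0.02 | 1.000 | 2.00 | 1.50 | 2.00 |

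In the raw comparison the added variance is thus 3%, 23% and 100%. At the middle the interval is √1.23 = 1.11 times as wide.

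**8. In participants.** Assume e = 0.02, a true RQ difference of 0.02, two-sided alpha 0.05 and 80% power. Then n = variance × (1.960 + 0.842)²/0.02².
- No diet noise: 0.0008 × 7.85/0.0004 = 15.7, so 16.
- d = 0.01: 20 raw, 19 with the covariate.
- d = 0.02: 32 raw, 24 with the covariate.

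The covariate recovers part of the loss, and most where diet noise is large. Subtracting the baseline removes the diet shift but adds the baseline's own error. Within the assumed range it never beats the raw comparison, and it equals it only at the top.

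**The case against.** **The text is incomplete.** Part of the document is not available and the analysis section breaks off mid-sentence. Diet instructions or baseline handling could stand in what is missing. This objection stands: the point is that neither is described in the available text. A reader might infer that diet was certainly neither recorded nor repeated, but the documents do not show that.

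**The baseline may already be used.** No placebo appears in the readable text, and a Dunnett procedure compares several means with one control, so the pre-dose reading may be that control. A shift that is constant within a visit cancels from comparisons with the same visit's baseline and from a dose-by-time contrast. This also stands, and it confines the concern to the raw between-dose comparison of levels. The baseline t-test does not close that gap. It looks at the mean difference, which can be near zero while individuals differ widely between visits, and it names only REE and RER.

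**The size is assumed.** A range of 3% to 100% cannot separate a trivial loss from a serious one. If the residual SD already reflected ordinary visit-to-visit variation, adding a diet SD would count diet twice. For that reason e is defined here to exclude diet.

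**Next-day visits.** Given "two visits per week with a minimum of 24 hours between visits", a reader might infer that the days before the two visits must differ because visit 1 takes up the day before visit 2. The text permits next-day visits but does not require them, and it does not say that food is withheld during the session. Any such difference would be a visit-order effect, which is a separate matter.

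**The aim is energy expenditure.** The ANOVA is introduced in those terms, and RMR is outside this point. But RQ, Fat% and CHO% are also listed as analysed, and no other comparison of the doses after dosing is readable for them.

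**Conclusion.** The concern holds as a loss of precision. The available text describes a 4-hour fast and no matching of the previous day's diet, while three analysed outcomes reflect fuel use. Under the stated assumptions the variance of the raw paired RQ difference rises by 3% to 100%, and by 23% at the middle. None of these inputs comes from the documents.

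A reader might infer that unmatched diet biases the dose comparison. It does not bias the mean difference, because dose order is randomised and blinded. Within-visit comparisons with baseline are largely protected, provided the diet shift is roughly constant over the session. This is a worthwhile, low-cost improvement; it does not invalidate the comparison.

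**What to change.** **For any visits still to be run.** The document is written in the past tense, so there may be none. If there are, ask participants to write down all food and drink, with type and amount, for the 24 hours before visit 1, or at minimum from the previous evening meal. Give them a copy to repeat before visit 2, and check the log on arrival. Flag clear departures before that visit's readings are seen. Use the flags only in a sensitivity analysis of RQ, Fat% and CHO%. The evening-meal minimum keeps this workable for next-day visits. The cost is a one-page log, a line in the instructions, a short check and a small burden on participants; no visit or test is added.

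**In either case.** Analyse post-dose RQ, Fat% and CHO% with the same-visit pre-dose value as a covariate. Fit participant as a fixed effect so that the slope is the within-person one. The pre-dose RQ is already measured at both visits; Fat% and CHO% should be available from the same reading, which should be confirmed. This needs no new data. State in the analysis section how the baseline enters the 100 versus 200 mg comparison. If diet records exist, report them; if not, give their absence as a limitation for the substrate outcomes.
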